4.3 Covariates

All analysis of covariance (ANCOVA) models and linear Mixed Model will include the baseline value of the variable as a covariate and treatment as class type fixed effects.

4.4 Handling of missing and incomplete data

Available data at each time point will be presented. The denominator for percentages will be based on the number of subjects in the appropriate treatment or cohort group for summary purposes.

4.5 Changes in the planned analysis

The primary endpoint and main secondary endpoints of the study are based on 12 week Induction Therapy data. After the last subject completes Part B of Induction Therapy, the study will be unblinded. A cut with 12 week data will be applied. Baseline characteristics, prior/concomitant medication, 12-week efficacy data, 12-week AE data and 12-week exposure data will be cleaned before unblinding. The list of efficacy and safety tables that will be produced with results of 12 week Induction Therapy data is provided in Section 9.4.1. Results of these analysis will be used to make a determination on whether or not KHK4083 meets the criteria for proof of concept of efficacy. Subjects that were enrolled per Protocol Amendment 1 and continued to be blinded in the Long Term Extension period will remain blinded. Also investigators will remain blinded for these subjects.

	Forms			
	Title	Statistical Analysis Plan Template		
	Code	Version	Effective Date	Page
	FRM_ST03_032	01	23 Apr 2015	24 of 53

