
Study Design:
 
This Phase 2, double-blind clinical study of multiple ascending doses of KHK4083 (or placebo) with an OLE Therapy phase will be conducted in approximately 60 randomized adult subjects with moderately active UC who have a documented unsuccessful previous treatment. The study will include a 4-week Screening Period, followed by a total of up to 64 weeks (treatment and follow-up) on study from the time of randomization to study completion. The Treatment Period includes double-blind Induction Therapy (12 weeks) and OLE Therapy (40 weeks) for eligible subjects at Week 12. Subjects already enrolled in the double-blind, long-term extension (LTE) under preceding versions of the protocol who worsen may be eligible to transition to the OLE up to Week 28. Selected Sponsor personnel will be unblinded after the last subject completes Induction Therapy. Post-treatment assessments will continue for 16 weeks after the last infusion associated with the subject's treatment period. The doses selected for this study are based on a Phase 1a/1b single-ascending dose study, which showed that KHK4083 was well tolerated and there were no dose-limiting adverse effects up to 10 mg/kg, the highest dose studied.
		

Name of Sponsor/Company: Kyowa Kirin Pharmaceutical Development, Inc.	Individual Study Table Referring to Part of Dossier in Which the Individual Study or Study Table is Presented: Volume: Reference:	(For National Authority Use Only)
Name of Finished Product: KHK4083		
Name of Active Ingredient: KHK4083		

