A subject's treatment assignment should only be unblinded by the Investigators and/or Sponsor's Medical Monitor when knowledge of the treatment is essential for the further management of the subject or may impact the safety of subjects in current and/or subsequent cohorts. Unblinding for any other reason will be considered a protocol violation.

The Investigators are strongly encouraged to contact the Medical Monitor before unblinding any subject's treatment assignment. However, the Investigator may unblind for safety reasons without prior notification, but must contact the Medical Monitor within one business day after the event and must document the unblinding in the subject's source records together with a completed SAE form. Any instance of unblinding will be reported in the clinical study report.

The Investigator or the designee who breaks the blind must record the date and the reasons as appropriate. In such cases, treatment with the investigational product must be stopped and the Sponsor must be contacted immediately to determine whether the subject should be withdrawn from the study. Every attempt should be made to contact the Sponsor before the blind is broken.

The study will be unblinded to select personnel from the Sponsor (or consultants acting on behalf of KKD) and/or from participating Contract Research Organizations. The individuals will be identified in the Blinding Plan and Unblinding Processes for Study 4083-002. The study will be blinded to all other study personnel/consultants, investigative site personnel, and study subjects.

After the last subject completes Part B of Induction Therapy, the study will be unblinded to additional select Sponsor personnel. The study will be unblinded to all study

personnel/consultants following database lock after the last subject completes the last follow-up visit.

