3.3 Randomization and blinding

After a subject meets all study eligibility requirements at Screening, the Interactive Response Technology (IRT) system will be used by the Investigator (or designee) to randomize the subject to double-blind Induction Therapy on Day 1 (Week 0). Subjects randomly assigned in Cohorts 1 - 3 will receive either KHK4083 (one of three dose levels) or placebo in a 3:1 ratio during Part A of Induction Therapy. Additional subjects (Cohort 4) in a 3:1 ratio will receive the recommended KHK4083 dose or placebo during Part B of Induction Therapy.

The subject, Investigator (or investigative site personnel) and KHK4083 study team at KKD will not know the treatment to which the subject is randomized during the double-blind Treatment Period. Placebo will be administered by IV infusion to each cohort to ensure blinded treatment. The study is being blinded to prevent bias in the safety evaluation, in particular the severity grading and causality determinations of AEs. However, at any time during the study, if a medical emergency occurs and subject treatment must be known, the blind may be broken according to the procedure described in protocol.

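### SAP 4.5 unblinds the study after Part B induction with one narrow exception, whereas Protocol 8.4 keeps every site and subject blind until final lock

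*SAP*

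**What the plan says.** **SAP 4.5 (Changes in the planned analysis).** The trigger is stated without a recipient: "After the last subject completes Part B of Induction Therapy, the study will be unblinded". A 12-week data cut follows, with the 12-week efficacy, adverse event and exposure data cleaned first. The section then names who stays blind: "Subjects that were enrolled per Protocol Amendment 1 and continued to be blinded in the Long Term Extension period will remain blinded". It adds: "Also investigators will remain blinded for these subjects". No other subject, site or Sponsor role is mentioned.

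**Protocol 8.4.** At the same time point: "After the last subject completes Part B of Induction Therapy, the study will be unblinded to additional select Sponsor personnel". For everyone else: "The study will be blinded to all other study personnel/consultants, investigative site personnel, and study subjects". General unblinding extends to all study "personnel/consultants following database lock after the last subject completes the last follow-up visit". The Synopsis agrees ("Selected Sponsor personnel will be unblinded after the last subject completes Induction Therapy"), as do sections 6.1 and 8.1.4.1.

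**SAP 3.3.** Subjects and investigators are to be blind during the double-blind Treatment Period, and the Sponsor is included: the "KHK4083 study team at KKD will not know the treatment to which the subject is randomized during the double-blind Treatment Period". The stated reason for the blind is to prevent bias in safety evaluation, in particular the grading and causality assessment of adverse events.

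**The concern.** Two current documents give different rules for one event. The SAP is the later of the two: Version 2 is dated 06 Oct 2017 and Protocol Amendment 2 is dated 04 Oct 2016. Its revision history lists unblinding at Week 12 as a reason for the new version, so a data manager or site-facing team could take SAP 4.5 as a deliberate change rather than loose wording.

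At stake are data collected after Week 12 that depend on the investigator's judgement and are still analysed by randomised arm. Adverse event severity and causality are the items that SAP 3.3 says the blind exists to protect. The Physician's Global Assessment is part of the partial Mayo score, which continues through follow-up.

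**Working it through.** There is no disputed calculation, so the check is mainly a comparison of texts. The few numbers only bound the size.

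1. **Planning figures.** Protocol 12.3.4: 51 evaluable / (1 − 0.15) = 60 randomised, as stated. Cohorts: 3 × 12 + 24 = 60, with placebo 9 + 6 = 15. Part B, enrolled last, is 18 + 6 = 24 subjects.

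2. **Scope of unblinding, side by side.**

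| | SAP 4.5 | Protocol 8.4 |
|---|---|---|
| Trigger | last subject completes Part B induction | same |
| Unblinded to | not stated | a further selected group of Sponsor staff |
| Subjects kept blind | Amendment 1 subjects still blinded in the LTE | all |
| Sites kept blind | investigators, for those subjects | all site personnel |
| General unblinding | not stated | after lock following the last follow-up visit |

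3. **What the exception implies.** If every site and subject stayed blind, as Protocol 8.4 requires, there would be no need to single out the LTE subjects and their investigators. Naming one group suggests that the others are not covered: Amendment 2 subjects in induction follow-up or the OLE, and any Amendment 1 subjects not in the blinded LTE.

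4. **Whether SAP 3.3 closes the gap.** It does not. Its promise runs only through the double-blind Treatment Period, so it reaches neither induction follow-up (Weeks 16, 20 and 26) nor the OLE. It also creates a second tension. The heading of Protocol 8.3 includes the LTE in the double-blind Treatment Period, so SAP 3.3 keeps the Sponsor study team blind while LTE treatment continues. SAP 4.5 unblinds the study during that time and lists only subjects and investigators as still blind. (SAP 4.1 also includes the LTE in its Double-Blind Therapy Period, but that is a category for tables and figures.)

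5. **Which later data depend on the arm.**
   - SAP 7.3: the mixed model compares partial Mayo change with placebo, with p-values, across double-blind therapy and its follow-up.
   - Protocol Table 9-1: the partial Mayo score with Physician's Global Assessment is recorded at Weeks 16, 20 and 26. By Protocol Appendix 2 the partial score has three subscores of 0 to 3, a maximum of 3 × 3 = 9, so the global assessment is up to 3/9, or one third.
   - SAP 9.4: adverse event tables by relationship and by maximum severity cover double-blind therapy plus follow-up.
   - SAP 4.1, Table 2: OLE summaries keep subjects randomised to placebo as their own category.

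6. **Upper limits on time.** Induction follow-up: Week 26 − Week 12 = 14 weeks. OLE with its follow-up: Week 64 − Week 12 = 52 weeks. Each applies in full only to a subject who is at Week 12 when the blind is lifted; subjects enrolled earlier have less follow-up left, or none.

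7. **What is untouched.** The trigger is the last subject completing induction, and the 12-week data are cleaned before unblinding. The primary and secondary efficacy endpoints are all at or before Week 12.

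**The case against.** The strongest reply is that SAP 4.5 concerns a data cut and a proof-of-concept decision, not site communication. It never says that sites or subjects will be told their assignment. The SAP states that it implements Amendment 2, sends the reader to the protocol for study conduct, and refers to the protocol for breaking the blind. The protocol says in four places that only selected Sponsor personnel are unblinded at this point, and treats unblinding outside its stated management and safety reasons as a violation. On this view, an unqualified SAP sentence gives no site permission to depart from the protocol, and all analyses are descriptive or exploratory in any case.

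Much of that stands. A reader might infer that release of assignments to sites is planned; the documents do not support that, and the risk is conditional on SAP 4.5 being followed literally. A reader might also take 14 and 52 weeks as actual exposure; they are ceilings, and in the OLE current treatment is already known to be KHK4083, so only the past induction arm could be newly disclosed. On SAP 3.3, it is fair to say that 4.5 is a later, specific change to a general statement and that Protocol 8.4 itself allows some Sponsor staff to be unblinded.

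The reply does not remove the mismatch. The SAP changed its text on this very subject after Amendment 2, and its only stated protection is narrower than the protocol's.

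**Conclusion.** The point holds as an inconsistency between two current documents, with a conditional risk to data after Week 12. If SAP 4.5 is applied as worded, adverse event severity and causality and the Physician's Global Assessment in induction follow-up, together with OLE ratings influenced by knowledge of the induction arm, could be recorded with the randomised arm known.

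The number of subjects affected cannot be derived: the documents do not give how many are in the LTE, how many late subjects enter follow-up only, or where each will be in the schedule when the blind is lifted. Part B's 24 subjects are the likeliest to be affected because they enrol last.

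Two stronger conclusions are not supported. The Week 12 efficacy result is not compromised, because those data are collected and cleaned first. Nor can it be said that the Blinding Plan already resolves the matter, or that the protocol requires the medical monitor and other named Sponsor roles to stay blind: Protocol 8.4 leaves the individuals to that plan, which is not among the documents.

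**What to change.** Amend SAP 4.5 to say that, after the last subject completes Part B induction, the study is unblinded only to the further selected Sponsor personnel allowed by Protocol 8.4. State that all investigators, site staff and subjects, whether in induction follow-up, the LTE or the OLE, remain blind to the induction assignment until final database lock, apart from the emergency provision already in 8.4.

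Revise SAP 3.3 so that its statement about the Sponsor study team agrees with the planned Sponsor unblinding while LTE treatment continues, with a reference to the Blinding Plan for the individuals concerned.

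This costs a few sentences in the SAP and changes no analysis, visit or sample size. If wider unblinding is intended, the cost is greater: the protocol needs an amendment, and efficacy and safety outputs that use data after Week 12 should be labelled as unblinded.

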4.6 Data Review Meeting

One data review meeting is planned before final database soft lock.

4.7 Software

Version 9.2 (or higher) of the SAS® statistical software package will be used to provide all summaries and data listings.

5. Evaluation of Demographic and Baseline Characteristics

5.1 Subject enrollment and disposition

The number of Subjects screened and in each visit week will be presented by treatment Cohort. Subject disposition will be summarized including the number and percentage of subjects enrolled and completed each of the study periods (Double-Blind Induction Therapy Period, Double-Blind Induction Therapy Follow-up Period, OLE/LTE Therapy Period, and OLE/LTE Therapy Follow-up Period), discontinued from the treatment, discontinued the study and completed the study. The number of subjects who moved from LTE to OLE Therapy Period. The definitions for completions and discontinuations are shown below;

- Subjects who have the CRF page of “Week 12” will be defined as those who completed Induction Therapy.
- Subjects who have the CRF page of “Follow-up 3 - Subjects not enrolling in LTE Therapy Period” or “Follow-up 3 - Subjects not enrolling in OLE Therapy Period” will be defined as those who completed Double-Blind Induction Therapy Follow-up Period.
- Subjects who have the CRF page of “Week 52” will be defined as those who completed OLE/LTE Therapy Period.
- Subjects who have the CRF page of “Follow-Up 3 - Post Long Term Extension Therapy” will be defined as those who completed OLE/LTE Therapy Follow-up Period.
- Subjects who have the CRF page of “End of treatment” will be defined as those who discontinued the treatment.
- Subjects who have “No” for the question of “Did the subject complete the study?” on the CRF page of “End of study” will be defined as those who discontinued the study.
- Subjects who have “Yes” for the question of “Did the subject complete the study?” on the CRF page of “End of study” will be defined as those who completed the study.

The number of subjects in the Safety Analysis Set and FAS will be provided. Disposition information will be provided overall and separately for each treatment Cohort.

	Forms			
	Title	Statistical Analysis Plan Template		
	Code	Version	Effective Date	Page
	FRM_ST03_032	01	23 Apr 2015	25 of 53

The reasons why subjects were excluded from any analysis set will be listed individually. In addition table summaries of the primary reason for discontinuation/withdrawal from the study will be presented by means of number and percentage of subjects by treatment cohort, period and overall.

5.2 Protocol deviations

Before unblinding, investigator and KKD will address all protocol deviations highlighted during the study a list will be presented in addition to a summary of the major and minor deviations from the protocol.

5.3 Demographics and baseline characteristics

Demographic characteristics (including age, race, ethnicity, and sex), height, weight, BMI (where BMI = Body weight (kg)/Height (m)²), duration of UC diagnosis, and Baseline values for UC assessment will be summarized by treatment Cohort using descriptive statistics in the Safety Analysis Set.

The following UC assessments scores will be provided:

1. Each subscore (for Mayo Clinic Score (0 to 3 for each subscore)
 - a. Stool frequency
 - b. Rectal bleeding
 - c. Modified Mayo endoscopy subscore (mMES)
 - d. Physician's global assessment
2. Ulcerative Colitis Endoscopic Index of Severity (UCEIS) Score (0 to 8)
3. Modified Baron Endoscopic Score (0 to 4)
4. Total Mayo Clinic Score (0 to 12) is the sum of stool frequency (subscore 0 to 3), rectal bleeding (subscore 0 to 3), mMES (subscore 0 to 3) and physician's global assessment (subscore 0 to 3).
5. Partial Mayo Clinic Scores (0 to 9) is the Complete Mayo Clinic Score without the mMES.
6. Total Inflammatory Bowel Disease Questionnaire (IBDQ) score is a quality-of-life assessment at Baseline. It is the sum of IBDQ Sub Scores.
7. Four IBDQ Sub Scores include bowel-related symptoms, systemic function, social function, and emotional status.

No statistical comparisons of differences in demographics/baseline data will be performed. Data listings will also be provided for all demographic information and baseline characteristics.

5.4 Medical, diet and surgical history

Medical history and concomitant diseases will be coded using MedDRA (version 18.1) and frequency distributions and percentages will be summarised by sequence for the Safety Analysis Set by System

	Forms			
	Title	Statistical Analysis Plan Template		
	Code	Version	Effective Date	Page
	FRM_ST03_032	01	23 Apr 2015	26 of 53

Organ Class (SOC) and Preferred Term. Medical history will be defined as the event that the answer for the question of “Ongoing at time of Informed Consent” on the CRF page of “Medical/Surgical History” is “No”. Concomitant disease will be defined as the event that the answer for that question is “Yes”.

Medical/surgical history and physical examination results of note, will also be listed by subject.

5.5 Prior and concomitant medications

Start and stop dates of medication or non-drug therapy will be compared to the start date of investigational product dosing to allow medications/treatments to be classified as either *prior* or *concomitant*.

Prior medications include any previous biologic treatment (for any indication), all treatment for UC taken within 6 months prior to Screening, and any other previous medication taken within 1 month prior to Screening. Concomitant medications include medications that started at any time and were taken at any time during the study including the follow-up period. Probiotic usage is to be tracked during the study.

If a start or stop date of medication or non-drug therapy is partial, the date will be compared as far as possible with the investigational product dosing start date. The medication or non-drug therapy will be assumed to be concomitant, unless there is clear evidence (through comparison of partial dates) to suggest that the medication stopped prior to the investigational product dosing start date. If the stop dates are missing, medications will be assumed to be concomitant.

The World Health Organization Drug Dictionary will be used to classify prior and concomitant medications by Therapeutic Class and Preferred Term. Prior medications will be summarized in the Safety Analysis Set. Concomitant medications will be summarized by each period (Double-Blind Induction Therapy Period, OLE Therapy Period, LTE Therapy Period, or Follow-up Period) in the Safety Analysis Set.

6. Evaluation of Treatment Exposure

6.1 Exposure to investigational product

Subjects who received investigational product are those who have the infusion initiation time recorded, and subjects who completed investigational product are those who have the completion time recorded. The definition of treatment duration in weeks will be derived from the recorded date and time of the IV infusion of investigational product as follow:

- Induction therapy: IV infusion of KHK4083 or placebo once every 2 weeks for a total of 6 treatments. For eligible subjects the first dose date for the Induction therapy is recorded at Day 1 (Week 0) after screening period; the last recorded dose date for the Induction therapy should be recorded at Day 71 (Week 10). Under this condition the treatment duration for the Induction

	Forms			
	Title	Statistical Analysis Plan Template		
	Code	Version	Effective Date	Page
	FRM_ST03_032	01	23 Apr 2015	27 of 53

- therapy is derived as $[(\text{last dose date of the Induction therapy} - \text{first dose date of the induction therapy}) + 1] / 7$, and the results will be expressed in weeks and rounded to the nearest integer.
- Long-term Extension Therapy (LTE): all the subjects who qualify and agreed to continue the treatment will receive 10 additional IV infusions of KHK4083 or placebo once every 4 weeks starting from Week 12 (+/- 7 days). Under this condition the treatment duration for the LTE therapy is derived as $[(\text{last dose date} - \text{first dose date of the LTE therapy}) + 1] / 7$, and the results will be express in weeks and rounded to the nearest integer.
 - Open-label Extension Therapy (OLE): all the subjects who qualify and agreed to continue the treatment will receive up to 10 additional IV infusions of KHK4083 once every 4 weeks starting from the first dose of the OLE therapy [“Week” of the first dose of the OLE therapy is different among subjects: Week 12 (+/- 7 days), Week 16 (+/- 7 days), Week 20 (+/- 7 days), Week 24 (+/- 7 days), or Week 28 (+/- 7 days)]. Under this condition the treatment duration for the OLE therapy is derived as $[(\text{last dose date} - \text{first dose date of the OLE therapy}) + 1] / 7$ results will be expressed in weeks and rounded to the nearest integer.
 - Overall: for subjects who had completed the Induction therapy and continued to the OLE or LTE therapy, the overall treatment duration under each investigational product administered will be derived as $[(\text{last dose date} - \text{first dose date}) + 1] / 7$, and the results will be expressed in weeks and rounded to the nearest integer.

The total dose administration is the sum of investigational product administered. The cumulative administered volume is the sum of dose of investigational product administered. Both the total administration and the cumulative administered volume will be derived by each treatment period (Double-Blind Induction Therapy Period, LTE Therapy Period, OLE Therapy Period, and Overall) as well as the duration of treatment.

Total dose administered, duration of treatment, and cumulative administered volume will be summarized by each treatment period (Double-Blind Induction Therapy Period, LTE Therapy Period, OLE Therapy Period, and Overall).

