8.1.4 Treatment Period (Weeks 0 to 52)

The 52-week Treatment Period (last dose Week 48) includes double-blind Induction Therapy over 12 weeks followed by OLE/double-blind LTE Therapy over 40 weeks. Subjects will continue in the study for 16 weeks after the last infusion associated with the subject's treatment period for on-site post-treatment assessments (refer to Figure 6.1-1 for overall study design). No other investigational or commercial agents or therapies other than KHK4083 and placebo and those described in Section 8.5 may be administered with the intent to treat the subject's UC.

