8.6.1 Study Visit Outside of Planned Scheduled - Delay in Dosing

During Induction Therapy, investigational product (KHK4083 or placebo) will be administered every 2 weeks, for a total of 6 doses. A visit window, ± 2 days at Week 2, and ± 4 days for all other doses, has been defined. If the study visit/dosing does not occur during the planned visit window, investigational product should not be administered at the visit and

the next dose should be administered at the next visit. KHK4083 or placebo should not be administered less than 6 days from the previous dosing.

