9.4 Tables

Number	Title
Table 14.1-1	Disposition of Subjects / Summary of All Subjects
Table 14.1-2.1	Demographic Characteristics / Safety Analysis Set
Table 14.1-2.2	Baseline Assessment of Ulcerative Colitis / Safety Analysis Set
Table 14.1-2.3	Demographic Characteristics / Full Analysis Set
Table 14.1-2.4	Baseline Assessment of Ulcerative Colitis / Full Analysis Set
Table 14.1-3.1	Prior Medications / Safety Analysis Set
Table 14.1-3.2	Concomitant Medications During Induction Period / Safety Analysis Set
Table 14.1-3.3	Concomitant Medications During Double-Blind Long Term Extension and Follow-Up Therapy / Safety Analysis Set
Table 14.1-3.4	Concomitant Medications During Open-Label Extension Therapy Period and Follow-Up Therapy / Safety Analysis Set
Table 14.1-4.1	Medical and Surgical History / Safety Analysis Set
Table 14.1-4.2	Concomitant Diseases / Safety Analysis Set
Table 14.1-5	Exposure to Investigational Product During Induction Therapy Period / Safety Analysis Set
Table 14.1-6	Exposure to Investigational Product During Long-Term Extension Therapy Period / Safety Analysis Set
Table 14.1-7	Exposure to Investigational Product During Open-Label Extension Therapy Period / Safety Analysis Set
Table 14.1-8	Exposure to Investigational Product During Study / Safety Analysis Set
Table 14.2-1.1	Summary of Baseline and Change from Baseline of Modified Mayo Endoscopy (MMES) / Full Analysis Set
Table 14.2-1.2	Change from Baseline in MMES at Week 12 / Full Analysis Set
Table 14.2-2.1	UCEIS During Induction Therapy Period / Full Analysis Set
Table 14.2-2.2	Total Mayo Clinic Score at During Induction Therapy Period / Full Analysis Set
Table 14.2-2.3	Partial Mayo Clinic Score at During Induction Therapy Period / Full Analysis Set
Table 14.2-2.4	Clinical Improvement at Week 12 / Full Analysis Set
Table 14.2-2.5.1	Change from Baseline in UCEIS at Week 12 / Full Analysis Set
Table 14.2-2.5.2	Change from Baseline in Total Mayo Clinic Score at Week 12 / Full Analysis Set
Table 14.2-2.5.3	Change from Baseline in Partial Mayo Clinic Score at Week 12 / Full Analysis Set

Forms

Title Statistical Analysis Plan Template

Code	Version	Effective Date	Page
FRM_ST03_032	01	23 Apr 2015	41 of 53

Number	Title
Table 14.2-3.1.1	Summary of Score and Change from Baseline in MMES During Long-Term Extension Therapy Period / Full Analysis Set
Table 14.2-3.1.2	Summary of Score and Change from Baseline in MMES During Open-Label Extension Therapy Period / Full Analysis Set

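### SAP 6.1 reports a treatment duration of 0 weeks after a single infusion, and gives an Overall duration only to subjects who continue beyond induction

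*SAP*

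**What the plan says.** SAP 6.1 uses one formula throughout: [(last dose date − first dose date) + 1] / 7. For induction, "and the results will be expressed in weeks and rounded to the nearest integer"; the LTE, OLE and Overall durations are rounded in the same way. The Overall duration is introduced "for subjects who had completed the Induction therapy and continued to the OLE or LTE therapy, the overall treatment duration", and the same sentence says it is derived for each product given. Section 6.1 then asks for total dose, duration and cumulative volume to be summarized by period and Overall. The matching whole-study table in SAP 9.4 is 14.1-8, "Exposure to Investigational Product During Study / Safety Analysis Set". SAP 4.2 places every subject who received even part of a dose in that set.

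Two other places bear on this. SAP 9.2 lists duration of treatment among the derived variables in days with no decimals, and states that this rounding is for listings and is not applied in the analyses. SAP 4.1, Table 2, keeps subjects randomized to placebo in a single placebo category during the OLE, and its third footnote acknowledges that they then receive KHK4083.

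**The concern.** A duration of 0 weeks for someone who was infused is not a sensible entry in an exposure table. The subjects it falls on include those who stop after a first infusion, who matter for infusion reactions and tolerability. The same zero appears for a subject who receives only the Week 12 infusion in the LTE and moves to the OLE at Week 16: the LTE duration is 0.

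The Overall rule is a separate gap. Stopping after induction is a designed path: Protocol 6.1.3 lets every qualifying subject decline further treatment, and others discontinue early. These subjects belong to the table's population but have no stated rule. If they are left blank, the summary describes only those treated longest. If a programmer fills them in, the definition is the programmer's and not the SAP's.

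**Working it through.** **Inputs**
- Formula and rounding: SAP 6.1.
- Induction schedule: "IV infusion of KHK4083 or placebo once every 2 weeks for a total of 6 treatments" (SAP 6.1), with the last dose on Day 71, Week 10.
- Induction dosing window: plus or minus "4 days for all other doses", and 2 days at Week 2 (Protocol 8.6.1). The same section bars dosing less than 6 days after the previous dose.
- OLE/LTE doses every 4 weeks from Week 12 to Week 48 (Protocol 8.1.4.2).
- Period lengths: "The 52-week Treatment Period (last dose Week 48) includes double-blind Induction Therapy over 12 weeks followed by OLE/double-blind LTE Therapy over 40 weeks" (Protocol 8.1.4).

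**The plan's own figure.** Study day = 7 × week + 1. For Week 10: 7 × 10 + 1 = 71. This reproduces the SAP's Day 71. The SAP states no resulting duration.

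**Formula applied on schedule**

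| Course | Days counted | Weeks | Reported |
|---|---|---|---|
| One infusion in a period | 1 | 1/7 = 0.14 | 0 |
| Two induction infusions (Days 1, 15) | 15 | 15/7 = 2.14 | 2 |
| Full induction (Days 1–71) | 71 | 71/7 = 10.14 | 10 |
| Full LTE or OLE (Weeks 12–48) | 253 | 253/7 = 36.14 | 36 |
| OLE entered at Week 28 | 141 | 141/7 = 20.14 | 20 |
| Overall (Weeks 0–48) | 337 | 337/7 = 48.14 | 48 |

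**Rounding.** With the Week 10 dose at the window limits, a full induction is 67/7 = 9.57 (reported 10) to 75/7 = 10.71 (reported 11). A zero arises only from a single infusion in the period: two doses 6 days apart already give (6 + 1)/7 = 1 week. Rounding otherwise moves a value by at most half a week.

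**6.1 against 9.2.** For the same one-infusion subject, 6.1 gives 0 weeks and 9.2 gives 1 day, carried into the analysis without approximation. The two sections cannot both be followed.

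**Overall summary.** An on-schedule continuer has 48.14 weeks. An induction-only completer would have 10.14 by the same formula but has no defined value. The documents give no continuation rate. For illustration, assume a share p of subjects continue, all continuers reach the Week 48 dose, and all others receive all six induction doses. The mean over everyone is p × 48.14 + (1 − p) × 10.14:
- p = 0.3: 21.5 weeks
- p = 0.5: 29.1 weeks
- p = 0.7: 36.7 weeks

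A continuers-only mean is 48.1 in each case, higher by a factor of 48.14/21.54 = 2.2 down to 48.14/36.74 = 1.3. The direction follows from the rule; the size depends on all of these assumptions and on non-continuers being left out.

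**The case against.** Much can be said for the plan. First-to-last-dose duration is a recognised convention and it is prespecified. The gaps of 10 against 12 weeks, 36 against 40 and 48 against 52 compare a dosing span with a period length, and the protocol itself separates the two by stating that the last dose falls at Week 48. Nor does the SAP say that the periods must sum to the Overall value, so 10.14 + 36.14 = 46.29 against 48.14 is not an error. All of that stands.

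A reader might go further and infer that study exposure, and with it the safety assessment, is misstated. The documents do not support that. Protocol 12.2.4 defines extent of exposure as the amount administered and adds the number of doses. SAP 6.1 summarizes total dose and cumulative volume by period and Overall, and Listing 16.2.5-3 shows number of doses beside duration. A one-infusion subject is therefore visible as dosed. SAP 8.1 classifies treatment-emergent events by onset date and reports subject counts, percentages and event counts. No exposure-adjusted rate is planned, so duration enters no safety result.

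One may also read the Overall sentence as merely explaining how to join periods, with induction-only subjects taking their induction value. That reading is reasonable, and no text excludes these subjects from the table. But the SAP does not state it, and the sentence as written limits the definition to continuers. Finally, 9.2 would remove the zero, but only by overriding 6.1.

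**Conclusion.** The point holds for the duration variable alone, in two respects. Under 6.1, any subject with a single infusion in a period is reported as 0 weeks, in conflict with 9.2. The Overall duration has no rule for early discontinuers or induction-only subjects, although Table 14.1-8 is on the Safety Analysis Set; followed literally, its summary covers continuers only and is shifted upward. The zero and the missing rule follow directly from the text. The size of the upward shift cannot be fixed from the documents; the factor of 1.3 to 2.2 is an illustration.

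Ending the count at the last infusion is a choice that needs a clear label, not a mistake. Amount-based exposure, number of doses and adverse event incidence are unaffected.

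A related inconsistency should be settled at the same time. Section 6.1 derives Overall duration by product given, whereas Table 2 keeps placebo-randomized subjects in one placebo category while they receive KHK4083 in the OLE.

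**What to change.** - Derive Overall duration for every subject in the Safety Analysis Set, from first to last dose in the study. For induction-only subjects this equals the induction value.
- Analyse duration unrounded, presented in days or in weeks to one decimal, and make 6.1 and 9.2 agree.
- Label the variable as first to last dose in tables and listings.
- Reconcile the by-product wording in 6.1 with Table 2, so that time on placebo and time on KHK4083 are shown separately for placebo subjects who enter the OLE.

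Optionally, add a second measure in which the +1 day is replaced by one planned dosing interval: 14 days in induction, 28 days in OLE/LTE, truncated at the next period's first dose or at end of study. On schedule this gives (70 + 14)/7 = 12, (252 + 28)/7 = 40 and (336 + 28)/7 = 52 weeks. It is an alternative convention and not a correction.

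The cost is SAP wording and one derived variable, with the affected shells updated. No new data are needed. If non-continuers would otherwise have been left blank, the reported Overall mean will be shorter.
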